10.2 Statistical Considerations for Phase Ib Dose expansion Study

If no MTD is observed with Level 1 through 3, we plan to continue/conduct the phase Ib dose expansion study as below. This expansion study is planned to understand and obtain initial efficacy data for the secondary endpoints.

Since the identical patient inclusion/exclusion criteria will be used in phase Ib dose expansion, all patient data from phase I dose escalation and phase Ib dose expansion studies can be combined for our statistical analysis, therefore, the required sample size of patients below will be both for phase I dose escalation and phase Ib dose expansion studies.

We obtained our statistical power and required sample size as a single-arm prospective study. In particular, for our evaluation of early efficacy we designed the study particular, for our evaluation of early efficacy we designed the study for testing $H_0: P \leq 0.10$ versus $H_1: P \geq 0.25$ at one-sided significance level 0.05 and power 0.80 as below.

P0	P1	Alpha	Beta	Cut-Off		Actual	Actual
				R + 1	N		
0.100	0.250	0.050	0.200	8	40	0.042	0.182

Where P0 is the maximum response proportion of standard care (tamoxifen alone), P1 is the minimum response proportion of our experimental treatment group, and N is the sample size.

For our statistical testing, if the number of responses $\geq R+1$, P0 is rejected based on Fisher's Exact test (34, 35). Alpha is the probability of rejecting that $P \leq P_0$ when this is true.

Beta is the probability of rejecting that $P \geq P_1$ when this is true.

Thus, the study requires 6 subjects under phase I dose escalation and 30 subjects under phase Ib dose expansion who will be treated with ribociclib (total 36) in order to test whether the proportion responding, P, is less than or equal to 0.100 or greater than or equal to 0.25. If the number of responses is 8 or more, the hypothesis that $P \leq 0.100$ is rejected with a target Type I error rate, α , of 0.050 and an actual error rate of 0.045. The null hypothesis will be rejected if 8 or more responses are observed in 40 patients. This design yields a type I error rate of 0.045 and power of 0.818 when the true response rate is 0.25.

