Phase I will be conducted in all patients with HR+/HER2- locally advanced or metastatic breast cancer with any prior endocrine therapy and up to three prior cytotoxic chemotherapy regimens administered in the metastatic or locally advanced setting.

Phase Ib dose expansion

Phase I trials are increasingly including dose-expansion cohorts (Ib) after the maximum-tolerated dose (MTD) has been reached to better characterize the toxicity profile and identify early signs of efficacy within this specific disease population. Our goal is to assess the anti-tumor activity Ribociclib + Tamoxifen and to further evaluate their safety in adult patients with HR+/HER2- locally advanced or metastatic breast cancer. Patients in the phase 1b expansion will have the same exclusion and inclusion criteria except that they will only be allowed to have up to two lines of cytotoxic chemotherapy in the metastatic setting.

Tamoxifen will be administered orally according to the standard regimen used in clinical practice (20 mg oral QD). Ribociclib will be administered orally, once daily for 21 consecutive days followed by a 7-day planned break (28-day cycle). In the *continuous dose cohort*, ribociclib will be administered daily (QD) without a break in each cycle. Tamoxifen will be administered in combination with ribociclib until disease progression or if unacceptable toxicity occurs that precludes any further treatment and/or if

treatment is discontinued at the discretion of the investigator or the patient, or the patient's death, whichever occurs first.

Phase I Study drugs (ribociclib dose may change depending on results of phase I)

TAMOXIFEN: 20 mg po daily

RIBOCICLIB: Phase I: starting at a dose of 400 mg po for 21 days of a 28-day treatment cycle; increased to 400 mg po daily (continuous dosing); increased to 600mg po daily for 21 days of a 28 day cycle.

Phase 1b expansion will look at two cohorts: 600 mg po for 21 days of a 28 day cycle with Tamoxifen and a continuous dosing cohort of ribociclib 400 mg daily with Tamoxifen.

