The **secondary objective** is to evaluate 2 dose expansion cohorts after the maximum-tolerated dose (MTD) has been reached to better characterize the toxicity profile and identify early signs of efficacy. Our goal is to assess the anti-tumor activity Ribociclib + Tamoxifen and to further evaluate their safety in adult patients with HR+/HER2- locally advanced or metastatic breast cancer.

To determine whether treatment with ribociclib improves response rate (RR) compared to the historical response rate with treatment with Tamoxifen alone. We know that the expected RR for Tamoxifen after failure of first line AI is about 10 % and therefore we hypothesize an improvement of RR to 25%.

Efficacy Evaluation

Response and progression will be evaluated in this study using the new international criteria proposed by the Response Evaluation Criteria in Solid Tumors (RECIST 1.1). This will be expanded in protocol.

DEFINITIONS:

DLT – Dose-Limiting Toxicity

MTD – Maximum tolerated dose

PFS – Progression-Free Survival

DDI – Drug-Drug Interaction

ER – Estrogen Receptor

PR – Progesterone Receptor

HER2 – Human Epithelial Receptor 2

PO – by mouth (per orum)

SERMS (selective estrogen receptor modulators)

SOC – standard of care

RR- Response Rate

FIH – First in human

Protocol:

The TEEL Study: A Phase I trial of Tamoxifen with Ribociclib (LEE011) in adult patients with advanced ER+ (HER2 negative) breast cancer.

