8 TREATMENT PLAN

Phase I/ Phase Ib dose expansion:

TAMOXIFEN: 20 mg PO daily will be given with RIBOCICLIB:

Ribociclib (LEE011)

In phase I: Ribociclib PO starting at a dose of 400 mg po for 21 days of a 28-day treatment cycle; this will be increased to 400 mg continuously. We will then evaluate 600 mg po daily for 21 days of a 28 day cycle if tolerated.

If there are no dose limiting toxicities, in the phase I portion, Tamoxifen 20 mg will be given with the MTD dose of Ribociclib in 15 patients. This is expected to be 600mg three weeks on and one week off. These patients will *not be stratified* for menopausal status.

If the 400mg continuous dose was well tolerated in the escalation arm, we will then expand this cohort in the phase Ib expansion, we will have an additional cohort of Tamoxifen 20 mg with 400 mg ribociclib in a continuous daily dose in an additional 15 patients. These patients will *not be stratified* for menopausal status.

Goserelin acetate (Zoladex) (3.6 mg subcutaneous every 28 days) will be given per NCCN guidelines to pre-menopausal and peri-menopausal. This will be given on day 1 of every cycle. We estimate that up to 20 of 40 patients on this protocol will require goserelin.

Goserelin is given if patient is premenopausal or peri-menopausal at the time of study entry.

Premenopausal status is defined as either:

- Patient had last menstrual period within the last 12 months.
- In case of therapy induced amenorrhea, with a plasma estradiol ≥ 10 pg/mL and/or FSH ≤ 40 IU/l or in the premenopausal range according to central laboratory definition.
- Patients who have undergone bilateral oophorectomy do not need goserelin.

Peri-menopausal status is defined as neither premenopausal nor postmenopausal (see exclusion criteria for definition).

8.1 Study Design:

Dose and Treatment Schedule – Table 8-1

No of pts	Cohort Level	RIBOCICLIB	Tamoxifen
3-6 (phase 1)	1	400 mg oral days 1-21, followed by 1 week break	20mg oral daily
3 -6 (phase 1)	2	400mg continuous	20 mg oral daily
3 -6 (phase 1)	3	600 mg oral day 1-21 followed by 1 week break	20 mg oral daily
15 (Ib dose expansion)	Phase Ib dose expansion	600 mg oral day 1-21 followed by 1 week break	20mg oral daily
15 (Ib dose	Phase Ib dose expansion-	400 mg oral daily	20 mg oral daily

expansion	continuous cohort	
------------------	--------------------------	--

Ribociclib Capsules/tablets for oral use 400 mg OR 600 mg Days 1-21 of each 28 day cycle or daily.

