10 STATISTICAL CONSIDERATIONS

10.1 Statistical Considerations for Phase I Study

A standard 3+3 design will be used (33) for the primary toxicity study under Phase I. A cohort of 3 patients will be recruited for each dose level at a time at a time. The first dose level will be level 1 and gradually increased to Level 2 and 3 if toxicity AEs are observed within the predefine statistical criterion/limit below.

Level 1: Ribociclib PO starting at a dose of 400 mg po for 21 days, followed by 1 week break of a 28-day treatment cycle;

Level 2: Ribociclib PO treated with a dose of 400 mg po daily for 28 days;

Level 3: Ribociclib PO treated with a dose of 600 mg po for 21 days, followed by 1 week break of a 28-day treatment cycle

If 1 patient out of 3 experiences a dose limiting toxicity (DLT; see below for definition) at level 1, 3 additional patients will be recruited at that dose level. If only 1 out of 6 patients in that dose level experiences a DLT, a new cohort of 3 patients will be treated with the next escalated dose level. That is, the dose escalation continues until at least two patients among a cohort of three to six patients experience dose-limiting toxicities (i.e., $\geq 33\%$ of patients with a dose-limiting toxicity at that dose level). If 2 out of 3 or 2 out of 6 patients experience a DLT, no further dose escalation will occur. The recommended phase II dose (RP2D) is defined as the dose level at which $\leq 1/6$ patients experience DLT. There will be no dose escalation beyond dose level 3, meaning that if $\leq 1/6$ patients experience DLT at this level, dose level will become the RP2D. No intra-patient dose escalation is allowed. Our dose escalation schedule follows a modified Fibonacci sequence in which the dose increments become smaller as the dose increases (e.g., the

dose first increases by 100% of the preceding dose, and thereafter by 50%, 33%, and 25% of the preceding doses). The RP2D will be defined as the dose level just below this toxic dose level.

Patients who achieve complete response (CR) or partial response (PR) or have stable disease (SD) may continue on study treatment until disease progression, as defined by RECIST v1.1 criteria, or intolerable toxicity.

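### Sections 8, 10.1 and 10.2 set inconsistent conditions for opening the phase Ib cohorts, so ordinary 3+3 results leave it unclear whether a cohort at the RP2D may open

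*Combined protocol and SAP*

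**What the plan says.** **Section 8 (Treatment Plan)** gives each expansion cohort its own condition.
- First cohort, 15 patients: "If there are no dose limiting toxicities, in the phase I portion, Tamoxifen 20 mg will be given with the MTD dose". That dose is expected to be 600 mg, three weeks on and one week off.
- Continuous cohort, 15 patients: "If the 400mg continuous dose was well tolerated in the escalation arm, we will then expand this cohort". No criterion is given for tolerability, and level 3 is not mentioned.

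**Section 10.1** contains the only numerical DLT rule.
- Escalation continues after 1/6 DLTs at a level.
- At level 3, with at most 1/6: "patients experience DLT at this level, dose level will become the RP2D".
- For a toxic level: "If 2 out of 3 or 2 out of 6 patients experience a DLT, no further dose escalation will occur", and then "The RP2D will be defined as the dose level just below this toxic dose level".

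**Section 10.2** opens with a condition on phase Ib as a whole: "If no MTD is observed with Level 1 through 3, we plan to continue/conduct the phase Ib dose expansion study as below".

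**The synopsis**, in its secondary objective, uses the opposite wording and plans to "evaluate 2 dose expansion cohorts after the maximum-tolerated dose (MTD) has been reached". A note under its dose table adds one fallback: if daily dosing suppresses the marrow too much, that arm changes to 400 mg on days 1-21.

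The definitions list only spells out the abbreviation MTD. No section states how the MTD is determined, and none says which opening condition governs.

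**The concern.** Section 8 treats the MTD as the dose to be expanded. Section 10.2 treats its absence as the reason to expand. If the MTD is the highest acceptable dose, section 8 makes sense, but 10.2 is not met in the expected case where 600 mg passes. If the MTD is a level found to be too toxic, 10.2 makes sense, but section 8 would dose a cohort at that level. No single meaning fits both.

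Separately, section 8 asks for no DLTs in phase I, whereas 10.1 tolerates one in six.

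The RP2D is a primary objective, and 30 of the 40 planned patients enter through this step. If the DLT results fall where the sections disagree, the site has to choose which section to follow after seeing those results.

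**Working it through.** **Inputs from the documents.** Three dose levels (Table 8-1). A level passes section 10.1 with 0/3 DLTs, or with 1/3 followed by 0/3 (that is, 1/6). Two or more DLTs in three or six patients make the level toxic.

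**Reading the rules against three results**

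| Phase I result | Section 10.1 | Section 8 | Section 10.2 |
|---|---|---|---|
| A: levels 1 and 2 pass, 1/6 at level 3 | RP2D is 600 mg | condition for the first cohort not met, read literally | met, if MTD means a toxic level |
| B: levels 1 and 2 pass, level 3 toxic | RP2D is 400 mg continuous | continuous cohort can open | go-condition not met, no other path given |
| C: 0/3 at level 3, but 1/6 at level 1 or 2 or both | RP2D is 600 mg | condition not met, read fully literally | met, as in A |

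**How often.** The plan states no probability to reproduce, and the documents give no DLT rates. I assume three sets of true rates for levels 1/2/3: 5% at each level, 10% at each level, and 10/15/20%. In B, 'well tolerated' is taken to mean that level 2 passed section 10.1.

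For a level with true DLT rate p:
- P(0/3) = z = (1-p)^3
- P(1/6) = s = 3p(1-p)^2 x (1-p)^3 = 3p(1-p)^5
- P(pass) = a = z + s

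| p | z | s | a |
|---|---|---|---|
| 5% | 0.857 | 0.116 | 0.973 |
| 10% | 0.729 | 0.177 | 0.906 |
| 15% | 0.614 | 0.200 | 0.814 |
| 20% | 0.512 | 0.197 | 0.709 |

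Results, computed from unrounded values:

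| Assumed rates | a1 x a2 | A = a1 a2 s3 | B = a1 a2 (1 - a3) | C = (a1 a2 - z1 z2) z3 |
|---|---|---|---|---|
| 5/5/5% | 0.948 | 0.110 | 0.025 | 0.182 |
| 10/10/10% | 0.821 | 0.145 | 0.077 | 0.211 |
| 10/15/20% | 0.737 | 0.145 | 0.215 | 0.148 |

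Worked example for 10/15/20%: A = 0.906 x 0.814 x 0.197 = 0.145; B = 0.906 x 0.814 x (1 - 0.709) = 0.215.

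**Consequence for the response test.** The section 10.2 table reproduces: 8 or more of 40 has exact binomial type I error 0.042 at a 10% response rate and power 0.818 at 25%.

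In result B, phase I holds 3 or 6 patients at each of three levels, so 9 to 18. Adding one cohort of 15 gives 24 to 33. The smallest cut-offs with type I error at most 0.05 are:

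| N | Cut-off | Type I | Power at 25% |
|---|---|---|---|
| 24 | 6 | 0.028 | 0.58 |
| 27 | 6 | 0.047 | 0.70 |
| 30 | 7 | 0.026 | 0.65 |
| 33 | 7 | 0.042 | 0.75 |

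These figures count every escalation patient as evaluable for response. Section 4 allows bone-only disease in escalation, so the usable number may be lower.

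**The case against.** **The clauses are go-conditions, not stops.** Sections 8 and 10.2 say when expansion proceeds; neither says what happens otherwise. A reader might infer that 10.2 shuts phase Ib after a toxic level 3. It does not say so, and section 8 gives the continuous cohort its own trigger. This stands: result B is an unmet condition with no stated path, not a prohibition. The inconsistency remains, because nothing says which section governs.

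**Section 8 can be read for its purpose.** Its wording may loosely mean that no level proved dose-limiting. It would then agree with 10.1, and also with 10.2 if MTD means a toxic level. That is probably the intent and weakens result C most, since closing 600 mg after 0/3 there is the least plausible reading. A reader might also add A, B and C to reach 0.32 to 0.51. That total depends on the fully literal reading of section 8 and on assumed rates, so it should not serve as the headline.

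**Some flexibility is already written in.** The synopsis says "ribociclib dose may change depending on results of phase I" and has the marrow-suppression fallback. Neither says when a cohort opens, but any new rule must respect the fallback.

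**Exposure at a toxic dose.** A reader might infer that the plan directs expansion at a dose shown to be toxic. The documents point the other way: 10.1 places the RP2D below a toxic level, section 8 only expects 600 mg, and the synopsis lets the dose change.

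**Conclusion.** The concern holds as an inconsistency between stated opening conditions, and it should be fixed. After 1/6 DLTs at 600 mg with the lower levels passed, following section 8 literally leaves closed a cohort at the dose that 10.1 has just named as RP2D. After a toxic level 3 with level 2 passed, 10.2 gives no route to expansion at the dose that 10.1 names.

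Under the three assumed sets of rates, the first result has probability 0.110, 0.145 and 0.145, and the second 0.025, 0.077 and 0.215. A further 0.182, 0.211 and 0.148 arises only if section 8 is read fully literally. These figures illustrate that the triggering results are ordinary; they do not predict what this trial will see.

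**What to change.** 1. In section 10.1, define the MTD/RP2D as the highest tested level with 0/3 or at most 1/6 DLTs.
2. Replace the opening conditions in sections 8 and 10.2 with one rule: each expansion cohort opens if its own dose level met that criterion. Define good tolerance of the continuous dose in the same way, and align the synopsis. The continuous cohort can then open on level 2 alone, and the 600 mg cohort stays closed if level 3 is toxic or untested.
3. Keep the synopsis fallback: if 400 mg continuous fails through marrow suppression, that cohort uses 400 mg on days 1-21, provided level 1 met the criterion.
4. If only one cohort opens, state the response cut-off for the resulting number of response-evaluable patients in place of 8 of 40.

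The cost is wording only. No level needs more patients than the 3+3 rule already requires. The rule does tie the first cohort to 600 mg, where section 8 says the MTD. If level 3 is toxic and level 2 passes, a first cohort moved to the MTD would only repeat the continuous regimen. The downside is that a one-cohort trial has lower power for response, about 0.58 to 0.75 with 24 to 33 patients, even if all escalation patients are evaluable.

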Patient Population:

Patients with estrogen and/or progesterone receptor positive, HER2-negative advanced (metastatic) breast cancer that are in one of the following populations

Pre-menopausal Women:

- A. Pre-menopausal women who received adjuvant Aromatase Inhibitor and Ovarian Suppression (AI + OS) in the adjuvant setting and completed at least 12 months of hormonal therapy.
- B. Pre-menopausal women who have never been treated with endocrine therapy with de-novo metastatic disease.
- C. Pre-menopausal women who have not received Tamoxifen in the metastatic setting, but have received up to two lines of chemotherapy for dose expansion and up to three lines for dose escalation.

Post-Menopausal Women or Men

- D. Post-menopausal women or men who have progressed on first-line or second-line therapy with an aromatase inhibitor
- E. Post-menopausal women or men who have recurred while on or after completion of adjuvant treatment with aromatase inhibitors (they have completed at least one year of adjuvant AI in the adjuvant setting before progression on AI).
- F. Post-menopausal women or men who are not considered candidates for treatment with an aromatase inhibitor by their oncologist, refused AI, or intolerant to AI
- G. Post-menopausal women or men who have been treated with up to two lines of chemotherapy for dose expansion and up to three lines for dose escalation in the metastatic setting.

Total number of patients: 40

Number of Centers: 1 (will be adjusted, increased if accrual goals are not met).

Sample Size Justification (will be updated by statistician):

For a total of **40 subjects**, about 9-12 will be accrued during phase 1 portion and **about 30 patients for the phase 1b expansion.**

Part 1: phase 1 portion:

We will evaluate the first 9-12 patients in the phase I portion for safety.
The Primary objective is safety.

Part II: phase Ib expansion:

For the phase one expansion we will include pre- menopausal women, post-menopausal women, and men evaluated as one group. We will further evaluate both a three weeks on and one week off cohort (i.e. once daily for 21 consecutive days followed by a 7-day planned break) and a *continuous dose cohort* of ribociclib administered daily (QD) without a break in each cycle. Tamoxifen will be administered daily per standard of care in both cohorts.

The **primary objective** in the phase I study is to confirm safety, tolerability, confirm DLT, and determine the RP2D of Ribociclib with Tamoxifen

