11.3 Evaluation of Best Overall Response

The best overall response is the best response recorded from the start of the treatment until disease progression/recurrence (taking as reference for progressive disease the smallest measurements recorded since the treatment started). In general, the patient's best response assignment will depend on the achievement of both measurement and confirmation criteria.

Note:

- Patients with a global deterioration of health status requiring discontinuation of treatment without objective evidence of disease progression at that time should be reported as "symptomatic deterioration". Every effort should be made to document the objective progression even after discontinuation of treatment.
- The best overall response for an early death, i.e., a patient who dies without documentation of disease progression and before it was time to conduct the first tumor reassessment, will be considered unevaluable or not assessed adequately. Response will also be considered unevaluable for any patient receiving treatment (regardless of how much was received) who did not have any follow-up assessment completed before initiation of alternative treatment. These patients must be replaced in both the phase I portion and the phase Ib expansion.
- In some circumstances, it may be difficult to distinguish residual disease from normal tissue. When the evaluation of complete response depends upon this determination, it is recommended that the residual lesion be imaged by PET scan or be investigated by fine needle aspirate/biopsy before confirming the complete response status.

Target Lesions	Non-target Lesions	New Lesions	Overall Response
CR	CR	No	CR
CR	Non-CR/Non-PD	No	PR
PR	Non-PD	No	PR
SD	Non-PD	No	SD
PD	Any	Yes or No	PD
Any	PD	Yes or No	PD
Any	Any	Yes	PD

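### Section 10.2 pools both phases on a premise of identical eligibility that Section 4 contradicts, and states 36 subjects beside a rule whose power holds only at 40

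*Combined protocol and SAP*

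**What the plan says.** **Pooling.** Section 10.2 combines data from escalation and expansion and applies one sample size to both. Its reason is "Since the identical patient inclusion/exclusion criteria will be used in phase Ib dose expansion".

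**Eligibility.** Section 4, shared items A.3 to A.5, sets different limits. Escalation accepts up to three prior chemotherapy lines in the metastatic setting and bone-only disease. Expansion accepts up to two lines and requires a measurable lesion by RECIST 1.1. The Synopsis paragraph on the phase Ib expansion also states the chemotherapy exception.

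**Size and rule.** Section 10.2 tests a response proportion of at most 0.10 against at least 0.25, one-sided at 0.05 with power 0.80. Its table gives N = 40, cut-off 8, actual alpha 0.042 and actual beta 0.182. The text then states the number needed: "requires 6 subjects under phase I dose escalation and 30 subjects under phase Ib dose expansion who will be treated with ribociclib (total 36"). It goes on: "The null hypothesis will be rejected if 8 or more responses are observed in 40 patients". The text gives the actual alpha as 0.045, twice, and power as 0.818. The Synopsis sample-size paragraph has a total of 40, of whom "about 9-12 will be accrued during phase 1 portion" and about 30 in expansion. Table 8-1 has three escalation levels of 3-6 patients and two expansion cohorts of 15.

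**Replacement.** Section 11.3 classes as unevaluable both early deaths and treated patients "who did not have any follow-up assessment completed before initiation of alternative treatment". It then says: "These patients must be replaced in both the phase I portion and the phase Ib expansion". Neither 11.3 nor 10.2 says whether the patients replaced still count in the response test.

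**The concern.** This is the plan's only formal efficacy test, and its stated error rates depend on who is counted and how many. The stated reason for pooling is wrong on the feature that matters most for a RECIST response, namely whether the patient has a lesion that can shrink measurably. The required number and the number in the rejection rule differ within one paragraph, and the stated power belongs to only one of them. With the response set also undefined, two analysts could follow the text, use different denominators with the same cut-off of 8, and reach different conclusions from the same data.

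**Working it through.** **Inputs.** Null rate 0.10, alternative 0.25, one-sided alpha 0.05, target power 0.80, N = 40 and cut-off 8 (Section 10.2); 36 = 6 + 30 (Section 10.2); escalation 9-12 (Synopsis); three levels of 3-6 (Table 8-1).

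**Formula.** With N patients analysed and cut-off c, alpha = P(X ≥ c) for X ~ Binomial(N, 0.10), and power = P(X ≥ c) for X ~ Binomial(N, 0.25).

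**Step 1: the plan's own figure.** N = 40, c = 8 gives alpha 0.0419 and power 0.8180 (beta 0.1820). The table's 0.042 and 0.182 and the text's 0.818 reproduce. The text's 0.045 does not.

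**Step 2: the 36.**
- N = 36, c = 8: alpha 0.0235, power 0.710.
- N = 36, c = 7: alpha 0.063, power 0.832.

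No cut-off at 36 meets both targets: 8 misses power, 7 exceeds alpha, a higher cut-off loses more power and a lower one adds more alpha.

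**Step 3: the 36 against the other counts.** Section 10.2 makes expansion follow the condition "If no MTD is observed with Level 1 through 3", and Section 10.1 recruits three patients per level. All three levels therefore imply at least 3 × 3 = 9 escalation patients. With 30 in expansion, pooling them all gives at least 9 + 30 = 39. The Synopsis gives 9 + 30 = 39 to 12 + 30 = 42, beside its total of 40.

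**Step 4: patients who cannot have a partial response.** Section 11.1.2 classes bone lesions as non-measurable. Under 11.2.1 and the table in 11.3, a partial response needs target lesions. For non-target disease, 11.2.2 leaves only disappearance of all lesions with normal tumor markers. Assume that m of the 40 cannot respond, so that power = P(X ≥ 8) for X ~ Binomial(40 − m, 0.25):
- m = 1 (39 patients): 0.794
- m = 2 (38 patients): 0.769
- m = 4 (36 patients): 0.710

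The documents do not give m. Section 11.6 accepts a bone lesion that is measurable on MRI, so not every bone-only patient need fall in this group.

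**Step 5: cut-off by number analysed.** The smallest c with exact alpha at most 0.05:

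| N analysed | Cut-off | Alpha | Power |
|---|---|---|---|
| 30-34 | 7 | 0.026-0.048 | 0.652-0.782 |
| 35-41 | 8 | 0.020-0.048 | 0.678-0.839 |
| 42-48 | 9 | 0.021-0.046 | 0.757-0.881 |

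A fixed cut-off of 8 keeps alpha within 0.05 up to N = 41 (0.0477). At N = 42 alpha is 0.054.

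**The case against.** **The rule itself is clear.** The table, the rejection sentence and the Synopsis total all say 40, and from 36 to 41 patients a cut-off of 8 holds alpha between 0.0235 and 0.0477. That stands, so the type I error is not at risk in this range. Power is: at 36 it is 0.710 against a target of 0.80.

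**The 36 may have a meaning.** Two regimens are expanded, so 6 + 30 could be three escalation patients at each of those regimens plus 15 + 15. The documents do not say this, and the same section combines all patient data. The conflict therefore remains, although this reading means that 39 is not the only possible minimum.

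**Replacement suggests an evaluable set.** Calling patients unevaluable and replacing them most naturally means 40 evaluable patients, which is a common choice in early-phase work. This largely stands. What is missing is the sentence that says so, and its consequence is that likely treatment failures leave the denominator.

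**Stronger readings that the documents do not support.**
- A reader might infer that replacement inflates the false-positive rate. That needs every replaced patient to be a non-responder and the historical 10% to be an all-treated rate. Neither is stated. On those assumptions, 2.5% replaced at N = 40 gives alpha 0.048 and 5% gives 0.054. The number replaced is unknown.
- A reader might take Table 8-1 to its maximum, 18 + 30 = 48, where a cut-off of 8 gives alpha 0.102. This needs all three levels to fill to six and conflicts with the stated total of 40.
- Section 3.1 mentions anti-tumor activity under the primary heading, and 3.2 does not list response. A reader might conclude that the test's status is open. The Synopsis, however, places the 10% to 25% comparison under the secondary objective, and 10.2 says that the expansion is to "obtain initial efficacy data for the secondary endpoints".

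**Conclusion.** The point holds, and the plan should be corrected before analysis. Two contradictions are firm and need no assumption: the identical-criteria premise against Section 4, and 36 against 40. At 36 with the stated cut-off, power is 0.710, not 0.818. The alpha of 0.045 is a plain discrepancy, since 0.042 is the value for 8 of 40.

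The loss of power from patients without measurable disease is real in direction, but its size rests on assumed counts and on those patients having no complete response. The denominator gap is secondary and its effect cannot be sized. The two effects pull in opposite directions: dropping early failures raises the observed rate, and including patients who cannot have a partial response lowers it.

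The stakes are limited. No stated dose decision depends on this test.

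**What to change.** In Section 10.2:

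1. Delete the identical-criteria premise and name one response set, for example all treated patients with baseline measurable disease from both phases. Report all treated patients as a sensitivity analysis.
2. Count patients in that set who die early or have no follow-up scan as non-responders. State here and in 11.3 that replacement does not remove the original patient. Give evaluable-only response as a further sensitivity analysis.
3. Reconcile 36 with 40 and with the escalation counts in the Synopsis and Table 8-1. Correct 0.045 to 0.042 for N = 40.
4. Replace the single cut-off with the table in step 5 of the working, and restate power for the expected number analysed.

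**Cost.** This takes rewording in 10.2, a sentence in 11.3, matching edits to the sample-size text in the Synopsis and, if the counts change, to Table 8-1. No extra accrual is needed if lower power is accepted and stated. That loss may not be trivial: power is 0.710 at N = 36. Keeping replaced patients can also carry N from 40 to 42, where the cut-off becomes 9 and power falls from 0.818 to 0.757. With these cut-offs, power reaches 0.80 only at N = 40-41 and again from N = 44 (0.806).
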